2.3 RISK/BENEFIT ASSESSMENT

2.3.1 KNOWN POTENTIAL RISKS

There are no known complications due to application of either a/LCI or OCT imaging techniques. Similar approaches have been previously approved by the UNC and Duke IRBs as non-significant risk device studies, and there were no safety issues in that study (UNC IRB# 07-1860).

Although the technique is not invasive, the probe itself will come in contact with esophageal tissue. For the dual modality probe (a/LCI-OCT) a small invagination in the surface of the instrument will mark the mucosa of the esophagus applied at the same location images are taken. This will aid in co-localization of research biopsies, to allow comparison of optical and histological diagnoses. We have used similar methodology in a previous study²⁶, with no adverse events noted. However, there is a theoretical risk of infection. To guard against this, the probe will be cleaned per current clinically approved methods for disinfecting endoscopy equipment which will utilize Cidex and/or Revital-Ox. Disinfection methods for this study have been reviewed and approved by the UNC Hospitals outpatient care and instrument reprocessing group. Refer to study standard operating procedures for additional information.

To date, there have been no adverse effects reported from exposure to the spectrum of light used in this device. Additionally, the device does not generate thermal injury, and because it is placed on the epithelial surface, and does not penetrate the tissue, no epithelial trauma is experienced. There is no risk of radiation from this device because the device uses only light waves.

Because the device is administered in conjunction with an upper endoscopy, there are a number of potential risks associated with the endoscopy that will be reviewed with subjects as part of their clinical care. There are also adverse events subjects may experience as a result of the endoscopy in which the contribution of the device may not be able to be ruled out. However, these events will be considered expected unless the nature, severity, or frequency implies the event is possibly related to the device itself (>50% likelihood that the event is related to the device or study procedures). These events include but are not limited to: throat irritation including scratchy or sore throat, esophageal pain, bloating, bleeding or tearing (perforation) of tissue in the esophagus, allergic reaction to the medication used for the endoscopy procedure (nausea, vomiting, fever, hypoxia (reduction in oxygen to tissues), pneumonia, adverse drug reactions, urine retention, clumsiness, drowsiness, blurred vision, and death), or aspiration of contents into the lungs. This may require the use of antibiotics, hospitalization and sometimes a surgery to repair.

The number of biopsies taken for this study is within the spectrum of routine clinical practice for esophageal diseases and Barrett's Esophagus in particular. Nevertheless, there is a very small risk of perforation or significant bleeding that would require a blood transfusion or other measures to stop the bleeding. To minimize this risk, subjects will be monitored for any bleeding during the biopsy portion of the procedure, and if bleeding is heavy, clinically indicated actions to stop the bleeding will be performed, and further biopsy procurement will be stopped. In the performance of esophageal research biopsies in greater than 5,000 patients previously, the investigators have not either had to perform endoscopic therapy to halt bleeding, nor has any patient experienced esophageal perforation.

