8.2.3 UNANTICIPATED ADVERSE DEVICE EFFECT

According to 21 CFR 812.3(s), an "unanticipated adverse device effect means any serious adverse effect on health or safety or any life-threatening problem or death caused by, or associated with, a device, if that effect, problem, or death was not previously identified in nature, severity, or degree of incidence in the investigational plan or application (including a supplementary plan or application), or any other unanticipated serious problem associated with a device that relates to the rights, safety, or welfare of subjects."

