8.2.4.2 RELATIONSHIP TO STUDY INTERVENTION

All adverse events (AEs) must have their relationship to study intervention assessed by an investigator who evaluates the event based on temporal relationship and his/her clinical judgment. The degree of certainty about causality will be graded using the categories below. In a clinical trial, the study product must always be suspect.

- **Definitely Related** – There is clear evidence to suggest a causal relationship, and other possible contributing factors can be ruled out. The clinical event, including an abnormal laboratory test result, occurs in a plausible time relationship to study intervention administration and cannot be explained by concurrent disease or other drugs or chemicals. The response to withdrawal of the study intervention (dechallenge) should be clinically plausible. The event must be pharmacologically or phenomenologically definitive, with use of a satisfactory rechallenge procedure if necessary.
- **Possibly Related** – There is evidence to suggest a causal relationship, and the influence of other factors is unlikely. The clinical event, including an abnormal laboratory test result, occurs within a reasonable time after administration of the study intervention, is unlikely to be attributed to concurrent disease or other drugs or chemicals, and follows a clinically reasonable response on withdrawal (dechallenge). Rechallenge information is not required to fulfill this definition. "Possibly related" means there is a reasonable possibility that the incident, experience, or outcome may have been associated with the procedures involved in the research. Reasonable possibility means that the event is more likely than not related to participation in the research or, in other words, there is a >50% likelihood that the event is related to the research procedures.
- **Somewhat Likely to be Related** – There is some evidence to suggest a causal relationship (e.g., the event occurred within a reasonable time after administration of the trial medication). However, other factors may have contributed to the event (e.g., the participant's clinical condition, other concomitant events), so there is a <50% likelihood that the event is related to the research procedures. Although an AE may rate only as "somewhat likely to be related" soon after discovery, it can be flagged as requiring more information and later be upgraded to "possibly related" or "definitely related", as appropriate.

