8.2.4.3 EXPECTEDNESS

The investigators will be responsible for determining whether an adverse event (AE) is expected or unexpected. An AE will be considered unexpected if the nature, severity, or frequency of the event is not consistent with the risk information previously described for the study intervention.

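### Section 2.3.1 settles expectedness by a >50% causality test, so a serious probe-associated event judged 50% or less likely to be device-caused could escape UADE evaluation

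*Combined protocol and SAP*

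**What the plan says.** Section 2.3.1 of the protocol describes adverse events that may follow the endoscopy and "in which the contribution of the device may not be able to be ruled out". The list is open-ended and includes bleeding and perforation of the esophagus. It then sets a default: "these events will be considered expected unless the nature, severity, or frequency implies the event is possibly related to the device itself". The parenthesis that follows defines possibly related as ">50% likelihood that the event is related to the device or study procedures". Within one sentence, then, the object of the causality judgement moves from the device alone to the device or study procedures.

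Four other places bear on the same classification:

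- Section 8.2.4.3 defines expectedness for the study generally: "An AE will be considered unexpected if the nature, severity, or frequency of the event is not consistent with the risk information previously described". The comparison is with the risk information for the study intervention, and likelihood of causation plays no part.
- Earlier in 2.3.1, the risk text for the technology itself reads "There are no known complications due to application of either a/LCI or OCT imaging techniques", and the section adds that the probe causes no trauma to the epithelium.
- Section 8.2.3, repeated in 8.3.1, takes the UADE definition from 21 CFR 812.3(s). It covers "any serious adverse effect on health or safety or any life-threatening problem or death caused by, or associated with, a device", provided that the effect was not already identified in the investigational plan. It contains no 50% threshold.
- Section 8.2.4.2, on relatedness, begins from the position that "In a clinical trial, the study product must always be suspect".

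**The concern.** Expectedness and relatedness are separate questions. The first asks whether an event of this nature, severity and frequency was foreseen in the risk information; the second asks whether the intervention brought it about. Section 2.3.1 answers the first by means of the second, and does so for exactly the events in which the device's part is uncertain. An investigator who cannot say whether the probe or the endoscope caused a perforation is directed to call it expected.

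At stake is what a UADE sets in motion under 8.3.3: an immediate sponsor evaluation, notice to participating investigators within 48 hours, and a report to the FDA, the reviewing IRBs and the investigators within 10 working days. If an event is labelled expected and regarded as already named in the plan, that sequence might not begin.

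**Working it through.** No sample size, power or error rate is involved, and the plan gives no figure to reproduce. The check takes a serious event on the 2.3.1 list, follows it through each rule, and asks where 2.3.1 by itself could change the outcome. The threshold is read as the parenthesis words it (device or study procedures), which lines up with the research procedures named in 8.3.1.

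**Step 1: the rules side by side.**

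- 2.3.1: expected by default; the default lifts above 50% likelihood of relation.
- 8.2.4.3: unexpected if inconsistent with the described risk information; no likelihood threshold.
- Unanticipated problem (UP), 8.3.1: must be unexpected, and related or possibly related (its own >50% bar), and serious or indicative of greater risk. All three are required.
- UADE, 8.2.3 and 8.3.1: serious, caused by or associated with the device, and not previously identified in the plan; no likelihood threshold.

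**Step 2: the four combinations.**

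| Judged likelihood of relation | UP | UADE |
|---|---|---|
| Above 50% | The 2.3.1 default lifts and the 8.3.1 relatedness criterion is met; 2.3.1 blocks nothing | The default lifts, and the plan identifies no trauma caused by the probe; 2.3.1 blocks nothing |
| 50% or less | Fails the 8.3.1 relatedness criterion whatever 2.3.1 says | The definition has no 50% bar, so the 2.3.1 default and listing could decide the outcome |

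Only the lower right cell depends on 2.3.1.

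**Step 3: a worked example in that cell.** Suppose a perforation occurs as the probe is passed and is judged 40% likely to be due to the paddle (the 40% is an illustration, not a figure from the documents). Under 8.2.4.2 it falls in the somewhat-likely category, which is below 50%. Under 2.3.1 it is expected. It is not a UP, and would not be one if 2.3.1 were silent, because 8.3.1 requires more than 50%. It is still a serious event associated with the device, so the UADE question turns on whether it was previously identified. One assessor can point to perforation in the 2.3.1 list and say that it was. Another can point to the statement, also in 2.3.1, that the probe causes no epithelial trauma and say that it was not. The first reading ends the matter; the second starts the 8.3.3 evaluation.

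**Step 4: the shifting object of the threshold.** Take an event attributed mainly to a research biopsy. It clears the bar if study procedures count, and does not if only the device itself counts. Two assessors could apply the sentence differently and both be following it.

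**The case against.** The strongest reply has three parts.

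First, 2.3.1 is itself risk information of the kind to which 8.2.4.3 refers, and both speak of nature, severity and frequency. A reader might infer a flat contradiction between them. The documents do not support that: expected under one and unexpected under the other follows only if the device-specific statements in 2.3.1 are taken alone as the risk information. What stands is that 2.3.1 conflates two concepts and the sections need reconciling.

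Second, the UADE definition does not use the word expected and does not refer to 2.3.1, so a careful assessor could apply it correctly as the text now stands. Perforation is also named as a biopsy risk later in 2.3.1 and in 2.3.3, so deleting one sentence would not remove it from the plan. Both points are right. They limit the finding to a possible misclassification, and they mean the fix must say what the list describes as well as remove the threshold.

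Third, safeguards exist. All adverse events are recorded regardless of relationship (8.2.5) and reported to the IRB under its requirements (8.2.6). The Independent Safety Monitor characterizes each for relatedness and expectedness within a week (10.1.6), and there is review at 3-month intervals (10.1.2). A reader might infer that the probe's safety would look clean by rule; these provisions rule that out. They do not replace the sponsor evaluation in 8.3.3, however, and the monitor would be judging expectedness under two differing rules.

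Three further inferences are tempting and fail. The sentence does not keep probe injuries out of UP reporting (Step 2). Death is not listed as a general procedural event: it appears only among reactions to the endoscopy medication. And the figure of less than 1/1,000 in 2.3.3 concerns bleeding from biopsies, so it cannot size the risk from passing the probe.

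**Conclusion.** The point holds in a limited form. Section 2.3.1 brings into expectedness a >50% causality test that neither 8.2.4.3 nor the UADE definition contains. It can matter in one situation: a serious event associated with the probe and judged 50% or less likely to be caused by it. Section 2.3.1 itself anticipates events whose device contribution cannot be excluded, so the situation is foreseeable. How often it would arise cannot be estimated, because the documents give no rate of serious events from passing the probe and do not say how often device and endoscope contributions could be told apart.

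The conclusion rests on two assumptions: that the 2.3.1 threshold is read with its parenthesis, and that an assessor might take a listing in 2.3.1 as previous identification in the plan. This is a wording fault worth correcting in a study of a newly developed probe. It does not show that safety monitoring as a whole is deficient.

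**What to change.** Reconcile the sections by wording alone:

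1. In 2.3.1, remove the >50% condition from expectedness. This also disposes of the mismatch between the device itself and the device or study procedures.
2. In 2.3.1, state that the list describes risks of the routine endoscopy and does not constitute previously identified effects of the probe.
3. State that expectedness is judged by 8.2.4.3 and relatedness separately by 8.2.4.2.
4. In 8.2.3 or 8.3.3, state that UADE determination follows the quoted definition in full, including the requirement that the effect was not previously identified, and without the >50% condition.

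Section 8.3.1 needs no change for UP reporting. The cost is protocol text, plus an occasional endoscopy-related serious event that receives a UADE evaluation and is found unrelated to the probe. Since the Independent Safety Monitor already classifies every event, no added staff should be needed.

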2.3.2 KNOWN POTENTIAL BENEFITS

This study will not likely result in immediate direct benefit to its participants. Because standard-of-care endoscopy will be performed regardless of imaging results, and because the imaging results from this trial will not be clinically actionable, immediate benefit in participation is not anticipated. However, should these imaging approaches be found to be an accurate, safe, and well-tolerated means of monitoring this patient population, several potential benefits would accrue to both study participants and others who undergo upper endoscopy. These individuals would have the option of a more efficient surveillance method.

2.3.3 ASSESSMENT OF POTENTIAL RISKS AND BENEFITS

There are no known complications due to application of the a/LCI or OCT imaging techniques, with similar approaches having been previously approved by the UNC and Duke IRBs as a non-significant risk device. The new instruments will again be evaluated by the IRB for application in this study.

The endoscopy referenced in this pilot study is performed as routine clinical care for patients and not specific to participation in this study, meaning subjects would undergo this procedure regardless of participation in this study.

Serious risk of endoscopic biopsies is very uncommon in subjects without known bleeding disorders and in those who do not regularly take blood thinning medications (such as aspirin, nonsteroidal anti-inflammatory medications, Coumadin (warfarin), Plavix, Lovenox, heparin, and low molecular weight

heparin). This is because the biopsies are very small (2-3 mm) and are obtained with blunt tipped forceps under direct vision of the physician performing the endoscopy. Possible serious complications include excess bleeding from the biopsy sites causing the blood pressure to drop and/or the need for blood transfusion or esophageal perforation (tear) due to trauma.

More common, but not serious, is minor bleeding which requires no treatment or responds to treatment with oral antacids. The risk of bleeding secondary to endoscopic biopsies is less than 1/1,000 and there is an even smaller risk of perforation or infection. When bleeding does occur, adequate medical staff and equipment are on hand to abate any long-term damage that could result from this risk. These participants will often already be undergoing biopsies as part of their standard of care so the incremental risk is expected to be minimal. The additional time necessary to complete biopsies for this study will be less than 2 minutes.

The Seattle biopsy protocol is used for standard of care (SOC) which includes taking 4 quadrant biopsies every one to two centimeters throughout the area of interest. Because we generally take these biopsies every two centimeters, up to 10 research biopsies in addition to SOC biopsies would generally be within the total number of biopsies advocated as the standard of care (give our mean BE segment length of 4-5 cm). It should also be noted that no higher incidence of complications has been documented by taking biopsies by the more aggressive biopsy protocol (4 biopsies every one cm) than the less aggressive (4 biopsies every two cm) protocol.

Given the excellent safety profile of these imaging techniques, the risks and costs inherent in the current standard of care, the potential benefits of this investigation outweigh the risks.

3 OBJECTIVES AND OUTCOMES

The purpose of this pilot study is to use the angle-resolved Low-Coherence Interferometry (a/LCI) and optical coherence tomography (OCT) technologies, developed by investigators on a small population of patients in an effort to gather information necessary for continuing development as a screening tool described above. Specifically, the study is designed to test the newly developed a/LCI-OCT device in human subjects to determine 1) whether adequate tissue contact can be attained to acquire high quality images, and 2) to identify if these images can discern whether the imaged tissue is squamous or BE epithelium.

4 STUDY DESIGN

4.1 OVERALL DESIGN

This is a pilot study to test the operating characteristics of a newly developed optical coherence tomography (OCT) device in human subjects, and to collect data for further optimization of the OCT device.

Phase II of the study will consist of a combined probe consisting of angle-resolved Low-Coherence Interferometry (a/LCI) with developed optical coherence tomography (OCT).

Potential subjects will be presenting to a UNC Endoscopy unit for routine care endoscopy for clinical signs or symptoms. If eligible, informed consent will be obtained prior to undergoing routine care upper endoscopy. During the endoscopy, and prior to taking any routine care biopsies, the probe will be attached to the end of the endoscope and passed with the endoscope into the esophagus. The probe will make contact with the epithelium of the esophagus, and data will be collected as part of this research study to identify operating characteristics of the new device. Esophageal images and pictures will be obtained during the procedure and will be used in this study.

In Cohort A, if biopsies are taken for routine care, then results from those biopsies will be used in this study. Slides may be requested from clinical biopsies for use in this study, after they have yielded their results for routine care.

In Cohort B, co-localized research biopsies may be taken at the same location the probe is deployed. The indentation on the surface of the probe leaves a transient raised area of mucosa, which will aid in endoscopic identification of the site and allow for targeted concurrent biopsies.

4.2 SCIENTIFIC RATIONALE FOR STUDY DESIGN

This is a pilot study to test the operating characteristics of a newly developed optical coherence tomography (OCT) and angle-resolved Low-Coherence Interferometry (a/LCI) imaging technologies in human subjects.

4.3 END OF STUDY DEFINITION

A participant is considered to have completed the study if he or she has completed all phases of the study including the last visit or the last scheduled procedure shown in the Schedule of Activities (SoA), Section 1.3.

The end of the study is defined as completion of the last visit or procedure shown in the SoA in the trial.

5 STUDY POPULATION

5.1 INCLUSION CRITERIA

Subjects must meet all of the following criteria to be eligible for this study:

1. Presenting to UNC for routine care upper endoscopy
2. Meet one of the following criteria:
 - 2.1. Cohort A
 - 2.1.1. Presenting to UNC for upper endoscopy of GI conditions without esophageal symptomatology with no history of gastroesophageal reflux disease (GERD) or other esophageal condition affecting the epithelium (asymptomatic controls). Esophageal

symptomology includes, but is not limited to, heartburn, globus, chest pain, dysphagia, and odonophagia OR,

- 2.1.2. Current dysplastic or non-dysplastic Barrett's Esophagus of any length OR,
- 2.1.3. History of dysplastic or non-dysplastic Barrett's Esophagus after treatment with endoscopic eradication therapy (EET)

OR

2.2. Cohort B

- 2.2.1. Current dysplastic or non-dysplastic Barrett's Esophagus of any length OR,
- 2.2.2. History of dysplastic or non-dysplastic Barrett's Esophagus after treatment with endoscopic eradication therapy (EET) OR,
- 2.2.3. Normal asymptomatic controls without any history of dysplastic Barrett's Esophagus

AND

- 3. Aged 18 to 80
- 4. Able to read, comprehend, and understand the informed consent document.

5.2 EXCLUSION CRITERIA

Subjects meeting any of the exclusion criteria below will not be eligible for this study:

1. Prior esophageal surgery (uncomplicated nissen fundoplication OK)
2. Pregnant women
3. Unable to provide written informed consent
4. History of esophageal stricture or prior esophageal dilation

Additionally, subjects meeting any of the exclusion criteria below will not be eligible for Cohort B of this study:

5. Uncontrolled coagulopathy

